## 5.3 Randomization

On Day 1, subjects who comply with all inclusion criteria and do not meet any of the exclusion criteria will be randomly allocated to one of the two treatment groups in a 1:1 ratio stratified by geographic region. Treatment assignment will be performed centrally using an interactive response technology system prior to the first intravenous infusion of IMP.

The investigator (or delegate) must log into the system using their own user identification number and a password. The investigator (or delegate) will enter the subject's number and other information required by the system to obtain a medication number. The medication number will then be used to select the correct package of IMP to give to the subject.

The subject's initial treatment will be blinded until the 26-week analysis. However, investigators and subjects will not be informed about the initial treatment allocation at any time before database lock of the full trial.

Randomization and blinding will be performed in accordance with the sponsor's standard operating procedures (SOPs).

## **6 OVERVIEW OF PLANNED ANALYSES**

### **6.1 Final analysis**

The primary analysis will be performed once all subjects have completed Visit 11 (Week 26), including database lock and unblinding. The results from this 26-week analysis will be reported in an interim integrated clinical trial report.

The final analysis of this trial, including Treatment Period B and Follow-up Period 2, will be performed after the last subject has completed the trial and the database has been locked.

### **6.2 Interim analyses**

An interim analysis is planned after a combined total of approximately 80 subjects in the 2 Phase III trials, KF7013-02 and KF7013-04, have completed Week 12 of treatment and the data is available in the databases. The interim analysis is for futility only and will be non-binding. The futility criterion will be based on the unblinded comparison of the primary endpoint and will be calculated using identical methods as for the final analysis. If the observed difference in the means of  $\mu_{400} - \mu_0$  is  $\geq -0.3$  points on the NRS, the null hypothesis will not be rejected and the recommendation will be to stop both trials. The interim analysis will be performed by an independent statistical analysis unit not otherwise involved in the conduct of the trial and the result will only state the recommendation to stop or continue the Phase III program. No unblinded information will be disseminated to the trial teams. Pending recruitment rates of both trials, it may be decided to forgo the interim analysis or conduct it at a different point in time. As the interim analysis will be for futility only, no inflation of the type I error will occur.

The interim analysis will be further described in a separate SAP as it will be performed on the pooled data of 2 trials.

## **7 DOCUMENT AND CHANGE HISTORY**

### **7.1 Changes in analysis compared to the trial protocol**

Not applicable.

Change from protocol	Rationale for change

Section 1.2 Trial objectives, endpoints, and outcomes
 
Other data to be collected that are not directly attributed to or considered as an endpoint
 
 
• Change from baseline to Week 6, Week 12, Week 26, Week 28, Week 36, and Week 52 in the responses to questions on the following questionnaires (recorded on the tablet computer): 
 
– Patient-Reported Outcomes Measurement Information System (PROMIS®)-29 profile version 2.0 (PROMIS-29 profile) (sub-scores: physical function, anxiety, depression, fatigue, sleep disturbance, social roles and activities, and pain interference). The change from baseline to Week 16 and Week 22 will be assessed for question number 29, GLOBAL07 only.
 
– Question EDDEP39 of the PROMIS Item Bank version 1.0 – Emotional Distress – Depression (PROMIS-EDDEP39) (not for Week 28).
 
– The 6 neuropathic pain items of the Short-Form McGill Pain Questionnaire 2 (SF-MPQ-2) (single items and the combined score).
 
– Pain Catastrophizing Scale (PCS) (not for Week 28).
 
– Pain Self Efficacy Questionnaire (PSEQ) (not for Week 28).
 
 
 
	
Schedule of events in protocol shows that these assessments are not done at Week 28.

Protocol Section 14.1.7.2 Analysis of the secondary endpoints
 
A logistic regression model will be fitted to the data, including the covariate baseline pain intensity score, and the factors geographic region, week, and treatment, and treatment-by-week interaction as fixed effects.
	
Change to logistic regression at respective weeks instead of longitudinal analysis to simplification of model fitting.

## 7.2 SAP amendment rationale

Not applicable.

---

## 8 ANALYSIS CONVENTIONS

### 8.1 General principles

All presentations will be done by treatment group.

Presentation of treatment groups will differ for the Week 1 to Week 26 and Week 27 to Week 52. Treatment groups for Week 1 to Week 26 are Placebo and Neridronic acid 400mg. For presentation of Week 27 to Week 52 in the final report, subjects will be displayed based on their treatment in Treatment Period A Placebo and Neridronic acid 400 mg and whether they have been treated with neridronic acid in Treatment Period B. Hence, for the final report, 4 treatment arms will be presented: Placebo, Placebo + Treatment Period B, Neridronic acid 400 mg and Neridronic acid 400mg + Treatment Period B and, if applicable, information will be summarized in an overall group.

The results from the 26-week analysis will be reported in an interim integrated clinical trial report. The display of the efficacy results in this report will be limited to all data up until Visit 11/Week 26, safety data will be reported for all data until the respective cut-off date. For the final ICTR, TFLs and analysis will be extended and additionally all data assessed after Visit 11/Week 26 will be analyzed and displayed.

The data collected and derived in the trial will be presented in subject data listings sorted by site and treatment.

Data collected in this trial will be summarized according to their nature as follows if not specified otherwise:

- Continuous variables: number of non-missing observations, arithmetic mean, standard deviation, minimum and maximum values, median and quartiles. If there are less than 5 observations, descriptive statistics will be presented based on the rules specified in Section 19.1.1.2.
- Categorical variables: absolute and relative frequencies. If not defined otherwise, the percentage denominator will be the number of subjects still in the trial (including missing values) at the respective time point in the analyzed population. The category missing will only be displayed if missing values occur.
- Time-to-event variables: Kaplan-Meier estimates together with the 95% confidence intervals (CI) and the hazard rate will be provided with the respective number at risk and the number censored at the relevant time points. In addition, the median time-to-event and its 95% CI will be presented if applicable. For calculating the survival estimate CI bounds, the log-log transformed estimate of CI bounds will be used. The time to event will be censored at the Visit 11 for the Week 26 report and End-of-Treatment Visit/End-of-Trial Visit for the final report if not otherwise specified.

Medical terms (e.g., prior and concomitant diseases, adverse events) will be coded via Medical Dictionary for Regulatory Activities (MedDRA). For the analysis, the primary System Organ Class SOC will be used. Medications will be coded according to World Health Organization Drug Dictionary (WHO-DD).

Table 1 shows the use of analysis sets in different analyses as defined in Section 9.

Table 1: Use of analysis sets

	Enrolled Set	Allocated Set	SAF	FAS	PKS	PDS
Subject disposition	X	X	X	X		
Discontinuations	X	X	X	X		
Protocol deviations			X			
Demographics			X	X		
Other baseline characteristics			X	X		
Subject medical and dental history			X	X		
CRPS history			X	X		
Prior and concomitant medication			X	X		
Exposure			X			
Compliance			X			
Primary endpoint				X		
Secondary endpoint				X		
Adverse events			X			
Laboratory values			X			
Pharmacokinetic concentrations					X	
Bone turnover markers						X
Soluble interleukin-2 receptor (sIL-2R)			X			
Other safety parameter			X			

FAS = Full Analysis Set, PDS = Pharmacodynamic Set, PKS = Pharmacokinetic Set, SAF = Safety Analysis Set

## 8.2 Definitions

### 8.2.1 Definition of subgroups

The following subgroups will be analyzed:

- Gender (male, female).
- Age (<65, >= 65).
- Region (USA/Canada, Europe, and Other Regions [including Asia-Pacific and Australia/New Zealand]).

Subgroup analyses will be limited to the primary endpoint and disposition and demographic information.

**8.2.2 Further definitions**

Baseline	
Baseline is defined as the last observation (scheduled or unscheduled) before first IMP administration if not otherwise specified. In general, baseline is the value recorded at Visit 2.
 
More precisely, for post-baseline comparisons of all parameters except pain intensity in the eDiary, the assessment before first IMP administration at Visit 2 (Day 1) will serve as the baseline based on recorded date/times. In case the value planned on Day 1 is missing or in case there are multiple values before first IMP administration on Day 1, the last scheduled or unscheduled non-missing value before first IMP administration will be used.
 
For current, average, and worst pain, baseline pain intensity will be calculated as the average of the non-missing pain intensity ratings obtained over the 7-day baseline pain assessment phase prior to first IMP administration.

Investigational Medicinal Products (IMP)	The IMPs used in this trial are neridronic acid and matching placebo.
On-treatment-period	For the purpose of this trial, the on-treatment period starts at the first IMP administration (included) and continues until the date (included) when the subject leaves the trial, i.e., at the Final Visit (Visit 17, week 52 after Follow up period 2) for trial completers, and otherwise at the End of Trial date for subjects not fully completing the trial. The on-treatment period extends beyond the dosing period. This is because of the persistence in bone and potentially prolonged effect of neridronic acid.
Pooling of sites	Individual sites will be pooled by geographic region. Geographic regions are defined as USA/Canada, Europe, and Other Regions (including Asia-Pacific and Australia/New Zealand).
Pre-treatment-period	Before the first IMP administration (excluded).
Treatment Period A completers	
Treatment Period A completers are treated subjects who completed IMP administration in Treatment Period A according to the protocol, i.e., subjects who received the full dose of all 4 planned infusions.
 
Subjects are identified via the “Treatment Period A completer” page in the CRF based on the data point “Did the subject complete the treatment?”

Follow-up Period 1 completers	Follow-up Period 1 completers are treated subjects who completed the Follow-up Period according to the protocol, i.e., subjects who have a Visit 11 not before Day 183. Subjects do not need to be Treatment A completers.
Treatment Period B	Treatment Period B completers are treated subjects who completed

---

completers	IMP administration in Treatment Period B according to the protocol, i.e., subjects who received the full dose of all 4 planned infusions.  Subjects are identified via the “Treatment Period B completer” page in the CRF based on the data point “Did the subject complete the treatment?”
Follow-up Period 2 completers	Follow-up Period 2 completers are treated subjects who completed the Follow-up Period 2 according to the protocol, i.e., subjects who have a Visit 17 not before Day 365. Subjects do not need to be Treatment Period A or Treatment Period B completers.
Trial completers	Trial completers are treated subjects who completed the trial according to the protocol. Subjects are identified via the End of Trial page in the CRF based on the data point “Trial fully completed?”  Subjects do not need to be Treatment Period A or Treatment Period B completers to fully complete the trial.

---

## 9 SUBJECT POPULATIONS

### 9.1 Enrolled Set

The Enrolled Set includes all subjects who signed the informed consent form.

### 9.2 Allocated Set

The Allocated Set includes all subjects who are allocated to treatment. Presentation of the Allocated Set will be conducted according to the allocated treatment.

### 9.3 Safety Set

The Safety Set (SAF) includes all subjects with at least 1 IMP administration including any partial infusion.

Analysis on the SAF will be conducted on the actual treatment received. Subjects that by accident switched treatment arm during the trial will be assigned to one treatment arm before unblinding.

### 9.4 Full Analysis Set

The Full Analysis Set (FAS) includes all subjects allocated with at least 1 IMP administration, including any partial infusion.

Analysis on the FAS will be conducted according to the allocated treatment.

### 9.5 Pharmacokinetic Set

The Pharmacokinetic Set (PKS) defines the subset of the subjects who have at least 1 evaluable pharmacokinetic concentration.

## 9.6 Pharmacodynamic Set

The Pharmacodynamic Set (PDS) defines all treated subjects with at least 1 non-missing value for at least 1 of the bone turnover markers.

## 10 DISPOSITION

### 10.1 Subject disposition

All presentations for subject disposition will be by treatment group and overall.

For describing the subject disposition, the following populations will be summarized, overall and for the following subgroups: gender, region and age group:

- Display with percentage denominator being the number of enrolled subjects.
  - Subjects enrolled (only overall).
  - Subjects enrolled but not allocated and reason for non-allocation (only overall).
- Displayed with percentage denominator being the number of allocated subjects. For the reasons for not being treated for subjects allocated but not treated, the percentage denominator is the number of allocated but not treated.
  - Subjects allocated (=Subjects allocated to Treatment Period A).
  - Subjects allocated but not treated and the reasons for not being treated.
  - SAF.
  - FAS.
  - Pharmacokinetic Set.
  - Pharmacodynamic Set.
  - Treatment Period A completers.
  - Follow-up Period 1 completers.
  - Treated in Treatment Period B.
  - Treatment Period B completers.
  - Follow-up Period 2 completers.
  - Trial completers treated only in Treatment period A.
  - Trial completers.
  - Subjects allocated and discontinued from IMP in Treatment Period A.
  - Subjects allocated and discontinued from the trial in Treatment Period A.
  - Subjects allocated and discontinued from the trial.
- Displayed with percentage denominator being the number of subjects allocated in Treatment Period B:
  - Subjects allocated in Treatment Period B.
  - Subjects allocated and treated in Treatment Period B.
  - Subjects allocated in Treatment Period B but not treated and the reasons for not being treated.

- 
- Treatment Period B completers.
  - Trial completers treated in treatment Period B.
  - Trial completers.
  - Subjects allocated and discontinued from IMP in Treatment Period B.
  - Subjects allocated and discontinued from the trial in Treatment Period B.

In addition, an overview table will be prepared presenting the number of subjects enrolled, allocated, in the SAF, and in the FAS per country and per site. Percentage calculation will be done in 2 ways:

- Denominator will be the number of all allocated subjects.
- Denominator will be the number of allocated subjects in the respective country and site.

## 10.2 Subject discontinuations

Discontinuations from the trial and from IMP will be presented for the SAF overall, per country and per site.

Reasons for discontinuations from the trial or from IMP will be presented for:

- Subjects discontinued from the trial.
- Subjects discontinued from IMP in Treatment Period A.
- Subjects discontinued from IMP in Treatment Period B.

Percentage denominator will be the number of subjects discontinuing in the respective group.

The details for “other reasons” will be presented in a frequency table, if applicable.

If more than 10% of subjects in the SAF discontinue the trial, the distribution of the time to discontinuation from the trial will be summarized using time-to-event methods. Time will be weeks until discontinuation.

## 10.3 Protocol deviations

Major protocol deviations will be presented overall and by site for the SAF. They will be grouped into categories as collected and summarized descriptively.

Major protocol deviations will be presented in a subject data listing sorted by site and treatment.

# 11 DEMOGRAPHICS AND OTHER BASELINE CHARACTERISTICS

No statistical tests for comparison of demographic and baseline data between treatment groups will be performed.

Subject demographics and baseline characteristics will be summarized descriptively by treatment group and overall.

Subject demographics and other baseline characteristics will be descriptively summarized for the SAF and the FAS. Subject demographics will also be presented for the enrolled set; presentation will be without treatment group but only for overall.

Furthermore, the subgroups will be displayed as defined in Section [8.2.1](#).

## 11.1 Subject demographics

Subject demographics are age [years], height [m], sex, race, ethnicity, and age group.

Age groups will be <18 years, ≥18 years and <65 years, ≥65 years and <85 years, and ≥85 years.

Remark:

Weight is recorded several times together with the vital signs parameters. Therefore, weight and the derived body mass index (BMI) will be described in the vital signs section below.

## 11.2 Other baseline characteristics

For parameters collected on more than 1 occasion during the trial including baseline, the assessment at baseline will be presented together with the assessments collected later in the trial rather than in a separate table for the baseline assessment only. These parameters are:

- Efficacy outcome parameters, e.g., pain intensities (current, average, and worst).
- Questionnaires and CRPS severity score (including signs and symptoms of CRPS).
- Laboratory parameters.
- Twelve-lead ECG parameters.
- Vital signs parameters.
- Bone turnover markers.
- Soluble interleukin-2 receptor.

## 11.3 Subject medical history

### 11.3.1 Medical history

Diseases and surgical interventions are presented as “prior” or “concomitant” as documented by the investigator.

Medical history will be summarized and sorted alphabetically, separately for prior and concomitant diseases, by SOC and Preferred Term (PT). The number of subjects will be displayed for each SOC and PT.

### 11.3.2 Dental history

Dental history will be summarized separately in the same way as the medical history.

Furthermore, the time since the last dental visit will be summarized.

### 11.3.3 Complex regional pain syndrome (CRPS) history

CRPS history will be descriptively summarized:

Continuous parameters based on date of Visit 1 are:

- Time since inciting or precipitating event (month) – if unknown presented as unknown.
- Time since onset of CRPS symptoms (month).
- Time since diagnosis of CRPS (month).

Categorical baseline characteristics are:

- 
- CRPS type (Type I, Type II, Unknown).
  - CRPS etiology.
    - Inciting or precipitating event (Missing, Known, Unknown).
    - Fracture, Sprain, Surgery, Crush, Others.
  - CRPS location (Left Body Site, Right Body Site, Upper Extremity, Lower Extremity, more than 1 Limb affected).
  - CRPS family history.
    - CRPS family history (No, Yes, Unknown).
    - Same limbs (No, Yes, Unknown).
  - Imaging method (None, Unknown, X-rays, Magnetic resonance imaging (MRI), Triple-phase bone scintigraphy, Other).

Except for inciting or precipitating event and family history multiple answers are possible.

#### **11.4 Prior and concomitant medication or therapy**

Prior and concomitant therapies will be descriptively summarized by category of additional therapy/treatment. Assessment of prior and concomitant will be done as described in the following for medications.

Prior and concomitant medication is collected in the e-CRF as per enrollment. For the analysis, the following algorithm will be used to define prior and concomitant medication:

- Prior is all medication stopped prior to the first dose of IMP, regardless of its start date.
- Concomitant is any medication not stopped before the first dose of IMP, regardless of its start date or medication started after the first dose of IMP.

Medication will be summarized and sorted alphabetically separately for prior and concomitant medication by Anatomical Therapeutic Chemical categories (Level 2: pharmacological or therapeutic subgroup and Level 3: chemical or therapeutic or pharmacological subgroup).

For each medication, the number of subjects will be displayed.

Medication or therapy started after last dose of IMP will be flagged in the subject data listing.

In addition, all newly prescribed opioid analgesic medication will be separately summarized overall and up to Week 26. Furthermore, the time to first newly prescribed opioid analgesic medication after first IMP will be summarized using time-to event methods. A newly prescribed opioid analgesic medication is any medication that is started after first IMP.

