 - Change from Week 26 in the EQ-5D-5L index score and the health-related VAS score.
 - Change from baseline in the responses to questions on the following questionnaires (recorded on the tablet computer):
 - Patient-Reported Outcomes Measurement Information System (PROMIS®)-29 profile version 2.0 (PROMIS-29 profile) (sub-scores: physical function, anxiety, depression, fatigue, sleep disturbance, social roles and activities, and pain interference). The change from baseline to Week 16 and Week 22 will be assessed for question number 29, GLOBAL07 only.
 - The 6 neuropathic pain items of the Short-Form McGill Pain Questionnaire 2 (SF-MPQ-2) (single items and the combined score).
 - Pain Catastrophizing Scale (PCS).
 - Pain Self Efficacy Questionnaire (PSEQ).
 - Response to Question EDDEP39 of the PROMIS Item Bank version 1.0 – Emotional Distress – Depression (PROMIS-EDDEP39) (recorded on the tablet computer).
-

-
- Concomitant analgesic medication use.
-

To describe the trial population and to evaluate subject eligibility

- Demographic data, medical history, dental history, CRPS history, prior medication and therapies, beta-human chorionic gonadotropin (β -HCG) pregnancy test, and drugs of abuse test.
-

To assess the safety and tolerability of neridronic acid in subjects with CRPS

- Adverse events, concomitant medications, physical examination findings, 12-lead electrocardiograms (ECGs), vital signs, body weight, and safety laboratory data.
-

To assess the pharmacodynamics of neridronic acid in subjects with CRPS

- Concentrations of bone turnover markers in serum: (C-terminal telopeptide of type I collagen [CTX], bone alkaline phosphatase [BAP], and procollagen type I amino-terminal propeptide [PINP]).
-

To assess the pharmacokinetics of neridronic acid in subjects with CRPS

- Concentrations of neridronic acid in plasma.
-

To assess health economics and work productivity (US sites only)

- Work Productivity and Activity Impairment Questionnaire: CRPS (WPAI: CRPS).
 - Medical resources utilization.
-

To explore markers for disease severity or progression in CRPS

- Concentrations of soluble interleukin-2 receptor (sIL-2R).
-

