1.4.2 Prior/concomitant medications or therapies

Subjects participating in the trial must be on stable therapy prescribed for CRPS, including any multidisciplinary treatment program (e.g., consisting of physical therapy, occupational therapy, cognitive behavioral therapy, and/or graded motor imagery, including mirror feedback). Initiation of a new interdisciplinary treatment program during the trial is prohibited. Other allowed therapies, such as spinal cord stimulation, may be continued during the trial if they are stable for at least 1 month prior to the start of treatment.

Subjects may continue treatment with allowed concomitant medications, including any stable analgesic regimens consisting of opioids and other analgesics, if they are on a stable, well-defined treatment regimen for at least 1 month before allocation to IMP and are anticipated to be able to maintain the treatment regimen up to and including Visit 8 at a minimum in the opinion of the investigator. A prescribed regimen including an as needed dosing schedule is permitted. A subject who does not take prescription analgesics but does take over-the-counter analgesics is permitted to participate if considered stable and anticipated to be able to continue taking only over-the-counter and non-prescription analgesics up to and including Visit 8 at a minimum. Over-the-counter analgesics must remain stable throughout the trial, up to and including Visit 8 at a minimum. After Visit 10, investigators should assess the further need of concomitant treatment for CRPS, in particular opioids, and evaluate if the dose or frequency of these treatments can be decreased, or if treatment can be stopped completely. Any resulting changes must be documented in the electronic case report form (eCRF). Subjects receiving treatment in Treatment Period B should remain on stable analgesic treatment (including over-the counter analgesics) between Visit 11 and Visit 16.

In the event a subject experiences a severe pain flare related to CRPS, trauma, or other reason, a course of short-acting analgesics, including opioids, may be prescribed for up to 2 weeks. The concomitant medication must be documented in the eCRF and the sponsor or sponsor's representative (i.e., medical monitor) must be notified.

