11.1.4.1 Visit 11 (Day 183 [Week 26]; +7 days)

Visit 11 must not occur prior to Day 183, to ensure a full 6 months of follow-up for all subjects.

If Visit 11 is not performed on Day 183, Visit 12 to Visit 15 should proceed in accordance with the originally scheduled time windows relative to Visit 11.

The following evaluations will be performed for all subjects:

- Record physical examination outcome (change from Visit 8).
- Record body weight.
- Record vital signs.
- Record concomitant medications and therapies.
- Assess further need of concomitant treatment for CRPS (in particular opioids), including decreases in dose or frequency as applicable.
- Record adverse events.
- Take blood for safety laboratory testing.
- Collect urine for quantitative urinalysis at the central laboratory.
- Perform dipstick urinalysis.
- Compliance assessment for electronic diary.
- Check trial discontinuation criteria (for details, see Section 9.3.1).
- Ask the subject to record the average, worst, and current pain on the tablet computer at the site.
- Measure edema, DMA, PPT, and AROM.
- Ask the subject to complete the EQ-5D-5L.
- Ask the subject to complete the PROMIS-29 profile and the PROMIS-EDDEP39 (the investigator should review the subject's answer to the PROMIS EDDEP39 question before the subject leaves the site and in case of suicidal ideation the investigator should consider involvement of a mental health professional).

-
- Ask the subject to complete the 6 neuropathic questions of the SF-MPQ-2.
 - Ask the subject to complete the PCS.
 - Ask the subject to complete the PSEQ.
 - Ask the subject to complete the PGI-S.
 - Ask the subject to complete the WPAI: CRPS (US sites only).
 - Collect information for medical resources utilization and health economics (US sites only).
 - Take blood for sIL-2R testing.
 - Take blood for omics testing.
 - Ask the subject to complete the PGIC.
 - Check the criteria to continue into Treatment Period B.

Decision to go into Treatment Period B

Compliance with the criteria to continue into Treatment Period B must be confirmed before allocation to IMP. The pain intensity question (question number 29, GLOBAL07) of the PROMIS-29 profile has to have a value of at least 4 at Visit 11. Subjects who do not meet the criteria to continue into Treatment Period B will continue with the Follow-up Period 2.

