12.2.2 Prior and concomitant medication or therapies

All medication requiring prescriptions (including oral contraceptives), over-the-counter medication (including herbals and vitamins), and therapies (including medical devices and therapies such as e.g., massage or cognitive behavioral therapy) used within 3 months prior to enrollment and up to the end of the trial must be recorded in the eCRF. All failed CRPS medication must be added in the eCRF (including medications stopped before 3 months prior to enrollment). Any change in dosage, regimen, frequency, or route, must be recorded in the eCRF as a new entry.

For the concomitant medication, the trade name, dose, dose unit, frequency, route, reason for use, start date, and stop date have to be recorded in the eCRF.

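### SAP 11.4's start-date rule for newly prescribed opioids also counts dose changes of an opioid the subject was already taking

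*SAP*

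**What the plan says.** Three rules meet here.

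- **Opioid review (Protocol 1.4.2).** After Visit 10, investigators should look at the need for CRPS treatment, opioids in particular, and "evaluate if the dose or frequency of these treatments can be decreased, or if treatment can be stopped completely". Protocol 8.2 repeats this. The Visit 11 procedures carry the item "Assess further need of concomitant treatment for CRPS (in particular opioids), including decreases in dose or frequency as applicable", and Visit 16 has the same item.
- **Data collection (Protocol 12.2.2).** "Any change in dosage, regimen, frequency, or route, must be recorded in the eCRF as a new entry". For concomitant medication, "the trade name, dose, dose unit, frequency, route, reason for use, start date, and stop date have to be recorded in the eCRF".
- **Analysis (SAP 11.4).** "all newly prescribed opioid analgesic medication will be separately summarized overall and up to Week 26", and the time to the first such medication is summarised with time-to-event methods. The definition is: "A newly prescribed opioid analgesic medication is any medication that is started after first IMP".

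Protocol 1.2 lists "Concomitant analgesic medication use" among the other data collected, under a heading which says that these items are not endpoints.

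**The concern.** The protocol foresees that some subjects will have their opioid dose lowered, and each such change produces a database row with its own start date after first IMP. The SAP classifies by start date and does not ask whether the subject was already on that opioid. A lower dose, which is a favourable change, and a higher dose, which is not, would then sit in the same count as a true new opioid.

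The dose changes need not be balanced between arms. Entry to Treatment Period B requires a pain rating of at least 4, and subjects in Period B should keep analgesics stable from Visit 11 to Visit 16. Those with most room to reduce after Week 26 are therefore largely those with less pain. If neridronic acid works, the mix of reductions and increases may differ by arm, and the opioid tables would be hard to read in either direction.

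**Working it through.** There is no figure in the plan to reproduce; the check is of a derivation rule.

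**Step 1: apply the rule to constructed records.** Day 1 is first IMP. Entries are built as Protocol 12.2.2 requires. The alternative rule counts an opioid as new only if the subject had no entry for that substance ongoing at first IMP.

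| Record | Entries starting after first IMP | SAP 11.4 rule | Alternative rule |
|---|---|---|---|
| Pre-existing opioid, unchanged | 0 | not counted | not counted |
| Pre-existing opioid, dose reduced on Day 160 | 1 | counted, event Day 160 | not counted |
| Pre-existing opioid, reduced in two steps from Day 160, then stopped | 2 | counted, first event Day 160 | not counted |
| Pre-existing opioid, stopped on Day 160 | 0 | not counted | not counted |
| Pre-existing opioid, dose increased on Day 100 | 1 | counted, event Day 100 | not counted |
| Opioid first started on Day 30 | 1 | counted, event Day 30 | counted, event Day 30 |

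The SAP rule cannot tell a reduction or an increase from a new start. It handles an outright stop correctly, because a stop closes an entry and opens none.

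**Step 2: look for a rule elsewhere that prevents this.** SAP 19.1.3.3 sorts medication into prior and concomitant by stop date and imputes missing start dates. It does not link successive entries of one drug. The general tables in SAP 11.4 count subjects by ATC category and medication, so they cannot show a change of dose.

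**Step 3: timing.** The planned opioid review begins after Visit 10 (Day 155) and Week 26 is Day 183: 183 − 155 = 28 days, or 4 of the 26 double-blind weeks. Protocol 8.2 allows other analgesic changes after Week 12. The overall summary and the time-to-event analysis in the final report run for longer.

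**Step 4: an illustration of size.** The documents give no opioid rates, so every input here is an assumption. Let *n* be the share with a true new start and *c* the share with a dose change of a pre-existing opioid (share on opioids × share of users with a change). If the two are independent, the reported share is *n* + *c* − *nc*. Take *n* = 0.08 on neridronic acid and 0.12 on placebo, a true difference of −4 points.

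- *A: 30% on opioids; reductions in 30% of active and 10% of placebo users.* Active: *c* = 0.09, so 0.08 + 0.09 − 0.0072 = 16.3%. Placebo: *c* = 0.03, so 0.12 + 0.03 − 0.0036 = 14.6%.
- *B: as A, with 50% on opioids.* Active: *c* = 0.15, so 0.08 + 0.15 − 0.012 = 21.8%. Placebo: *c* = 0.05, so 0.12 + 0.05 − 0.006 = 16.4%.
- *C: as A, plus increases in 5% of active and 25% of placebo users, in different subjects from the reductions.* Users with a change: 35% in each arm, so *c* = 0.105. Active: 0.08 + 0.105 − 0.0084 = 17.7%. Placebo: 0.12 + 0.105 − 0.0126 = 21.2%.

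In A and B the sign of the difference reverses. In C it does not (17.7 − 21.2 is about −3.6 points before rounding), although both percentages are well above the true 8% and 12%.

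**The case against.** The strongest reply is that the SAP speaks of a medication that is started, not of an eCRF entry. In ordinary language, lowering the dose of a drug in use starts nothing, and a programmer might collapse entries by substance. That reading is possible, but it is written nowhere; with data held as one row per dose and a rule based on start date, the literal derivation is the other one. Nor does the SAP's reference to the protocol of 14 March 2018 explain the gap: the amendment log shows the new-entry requirement already in the text before Amendment 01.

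Other parts of the defence stand, and they limit what may be inferred.

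- A reader might infer that the protocol orders sites to taper opioids. It does not: the wording is to assess and evaluate, as applicable, and Protocol 3.2 defines should as a recommendation.
- A reader might infer that an efficacy endpoint is damaged. Analgesic use is not an endpoint; Amendment 01 added it to Section 1.2, and the list in SAP 4 omits it. SAP 11.4 is descriptive.
- A reader might infer that a true opioid-sparing effect would be reported with the wrong sign. That follows only from assumptions such as A and B, which leave out dose increases; C, which is no less plausible, gives no reversal.
- A reader might infer that opioid reduction could not be seen at all. Doses and dates are collected, SAP 8.1 provides subject listings, and Protocol 14.1.6 promises a special focus on analgesics and allows further summaries. What is missing is a planned SAP summary of dose changes.

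**Conclusion.** The point holds as a misclassification. SAP 11.4's definition, applied to entries as Protocol 12.2.2 has them recorded, counts reductions and increases of a pre-existing opioid as new prescriptions and as time-to-event events. The overall, Week 26 and time-to-event summaries therefore mix true new starts with dose changes in either direction. This rests on the entries not being collapsed by substance before the rule is applied, and the SAP has no instruction to collapse them.

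The size and direction of the bias cannot be determined from the documents. Exposure to the planned opioid review is about 4 weeks in the Week 26 summary and longer in the final report. The primary analysis and the confirmatory secondary analyses do not use this variable and are unaffected. The definition should be corrected before unblinding.

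**What to change.** In SAP 11.4:

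1. Define a newly prescribed opioid as an opioid substance started after first IMP for which the subject had no entry ongoing at first IMP.
2. Link successive entries of the same substance within a subject, so that a change of dose, regimen, frequency or route continues an existing treatment.
3. Run the summaries (overall and up to Week 26) and the time-to-event analysis on that definition.
4. For opioids ongoing at first IMP, count subjects with a dose decrease or stop, and subjects with an increase, separately by arm.

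A switch to a different opioid would still count as new under item 1; the SAP should say whether that is intended.

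The cost is a few lines of SAP text and a little medication programming. Dose, unit, frequency, route and dates are already collected. Conversion to oral morphine equivalents is optional: within one substance and route, the direction of a change can usually be read from dose and frequency.
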